**11.0 Statistics**

**12.0 Publication**

**13.0 References**

**14.0 Appendix**

14.1 Prothym – transthoracic echocardiogram (TTE) protocol

14.2 Performance status

14.3 CTC version 4.0

14.4 Masaoka-Koga staging system

14.5 WHO classification system of thymoma

## 1.0 Synopsis

Title of study	PROTHYM Trial  Proton radiotherapy of thymic malignancies  The study is supported by SLUSG, Swedish Lung Cancer Study Group
Principal investigator	[name] MD PhD
Co-investigators	[name] MD [name] Med Phys. PhD [name] MD [name] MD [name] [name] [name] [name] [name] MD [name] [name] [name] MD [name] [name] [name] MD [name], PhD
Study centres	Skandion Clinic, Uppsala, Sahlgrenska University Hospital, Gothenburg, Karolinska University Hospital, Stockholm, Akademiska Hospital, Uppsala, Norrlands University Hospital, Umeå, Örebro University Hospital, Linköping University Hospital, Skåne University Hospital, Lund
Study phase	Prospective, non-randomized phase II study
Number of patients	40 patients
Study Start	Sep 2017
Planned study period	Recruitment Start Date : Sep/2017 Target recruitment period:60 months Sep/2022) Follow up period. End date: 5 years from last treatment.
Study objectives	Primary : Toxicity (e.g. cardiac and pulmonary toxicity) and Local control at 5 year Secondary : PFS

	
Overall survival
 
Quality of life, measured by EORTC QLQ 30 + LC 14
 
Relapse pattern

Study design and plan	
This is a multicentre non-randomized phase II study of proton beam radiotherapy in patients with thymic epithelial tumours (i.e. thymoma and thymic carcinoma) in the post-operative setting or in inoperable patients with localized disease.
 
Patients not willing or for any reason unsuitable to undergo proton treatment will be asked to participate in a follow-up assessment after the regular photon treatment in the same manner as the included patients.

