### **5.3 Treatment Schedule**

The study population will consist of three patient categories;

**A** patients who have undergone radical surgery

**B** patients who have undergone non-radical surgery

**C** patients who are considered inoperable.

Radiotherapy doses will differ between the groups. We have assumed that RBE for protons is 1.1 and the prescribed dose is the corresponding dose for photons (Gy(RBE)). Within brackets is the physical dose.

Patients who have undergone radical surgery but has an unfavorable histology (B2, B3, C) and/or Masaoka stage III or IVa (selected stage II-patients can be considered according to local practice) will receive 2 Gy(RBE) once daily, five days a week to a total dose of 50 Gy(RBE) (1.82 Gy OD, total dose 45.5 Gy)

Patients who have undergone non radical surgery (R1), regardless of stage and histology, will receive 2.3 Gy(RBE) once daily, five days a week, to a total dose of 57.5 Gy(RBE) (2.09 Gy OD, total dose 52.25 Gy)

Patients who are considered medically inoperable, or refuses surgery, regardless of stage and histology, and patients who have undergone R2 non-radical resection will receive 2.5 Gy(RBE) once daily, five days a week, to a total dose of 62.5 Gy(RBE) (2.27 Gy OD, total dose 56.75 Gy)

Patients not willing to participate in study, but willing to be included in follow-up according to study protocol will receive photon therapy according to local practice. The total dose must be  $\geq 45$  Gy.

Up to three cycles of chemotherapy may be administered prior to start of radiation according to local practice. Radiation therapy shall then start within 4-6 weeks after completion of the third cycle. Use of concomitant chemotherapy is not allowed.

If surgery has been performed, radiation therapy shall start 4-8 weeks thereafter

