## 8.0 Radiotherapy

All patients included in the study must be able to receive prescribed dose to the target volume without exceeding absorbed doses to the organs at risk. Dose planning shall be performed with a CT-based system. A 4DCT for the planning is mandatory and has to be repeated before start of treatment. If tumour motion exceeds 0.5 cm proton therapy will not be given. All patients needs to have a photon backup plan, preferably with IMRT/VMAT technique although 3DCRT is allowed. Treatment planning can be performed on either average CT from the 4D-CT or a regular CT. Slice thickness is to be maximally 3 mm. If the photon plan is superior to the proton plan, the photon plan is to be used and the patient will be excluded from the study and followed up according to the photon cohort protocol.

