## **9 Adverse events**

### **9.1 Definition**

#### **Adverse events (or adverse experience) (AE):**

An AE is any untoward medical occurrence in a subject or clinical investigation subject treated within a study protocol and which does not necessarily have a causal relationship with this treatment.

An AE can therefore be any unfavorable and unintended sign (including an abnormal laboratory finding, for example), symptom, or disease temporally associated with the radiation treatment, whether or not considered related to the radiotherapy

Due to regulatory requirements, events occurring during pre- and post-treatment periods should also be designated as AEs. Therefore, safety surveillance - reporting of (S)AEs - commences at the time when the subject is enrolled into the study (date of signature of the informed consent) until the End of Study Visit has been performed.

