## **9.2 Recording of Adverse Events**

All AEs must be documented in the appropriate section of the CRF. For SAEs, a SAE report form (initial or follow up) must be completed in addition.

The following aspects must be recorded for each event in the CRF:

- A description of the AE in medical terms, not as reported by the subject;
- The date of onset (start date)
- The date of recovery (stop date)

At each contact with the subject, the investigator must seek information on adverse events by specific questioning and, as appropriate, by examination. Information on all adverse events should be recorded immediately on the Adverse Event module of the CRFs using the CTCAE Version 4.0

A written version will be available at each study site, see also. CTCAEv4.0.

Version 4.0 <http://ctep.cancer.gov/reporting/ctc.html>

Serious adverse events should be noted on the Serious Adverse Event Report form.

All adverse events occurring during the study period must be recorded. The clinical course of each event should be followed until resolution, stabilisation or until it has been determined that study treatment or participation is not the cause. Serious adverse events, which are still ongoing at the end of the study period, must be followed up to determine the final outcome.

Any serious adverse event, which occurs after the study period and is considered to be possibly related to study treatment or study participation should be recorded and reported immediately.

The grade as assessed by the investigator according to the definitions in CTCAE v4.0.

Grade 1 = mild

Grade 2 = moderate

Grade 3 = severe

Grade 4 = life-threatening or disabling

Grade 5 = death related to AE

- The causal relationship to therapy as assessed by the investigator; the decisive factor in the documentation is the temporal relation between the AE and the study drug. The following judgments of the causality to study procedures are to be used:

**Not Related**; There is not a temporal relationship to study treatment.

**Not Likely**; There is a temporal relationship to study treatment, but there is not a reasonable causal relationship between the treatment and the AE.

**Possible**; there is a reasonable causal relationship between the study treatment and the AE.

**Probable**; there is a reasonable causal relationship between the study treatment and the AE.

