## **11.0 Statistics**

We will perform a Kaplan-Meier analysis with the aim to compare our data with published historic data from the ITMIG international database and other datasets. Since there is a limited amount of published thymoma data concerning heart we will also try to relate heart toxicity with published data from Hodgkin and breast cancer studies. Toxicity data will be analysed descriptively and there will be a comparison between the proton patients and photon control group. 40 patients will be included in the study

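### The protocol does not secure equal collection of harms in proton patients and in the photon controls with whom Section 11 compares their toxicity

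*Protocol*

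**What the plan says.** Section 11 states that "there will be a comparison between the proton patients and photon control group". Toxicity is a primary objective in the synopsis and in Section 4.1.1.

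The photon group is described in three places:

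- Synopsis, study design: patients unwilling or unsuitable for protons "will be asked to participate in a follow-up assessment after the regular photon treatment in the same manner as the included patients".
- Section 5.3: "Patients not willing to participate in study, but willing to be included in follow-up according to study protocol" receive photons by local practice.
- Section 8.0: if the photon plan is better than the proton plan, "the patient will be excluded from the study and followed up according to the photon cohort protocol". The document does not mention that cohort protocol again.

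Section 9.1 defines an adverse event as "any untoward medical occurrence in a subject or clinical investigation subject treated within a study protocol". It says that surveillance "commences at the time when the subject is enrolled into the study", takes the consent signature as the enrolment date, and runs surveillance to the End of Study Visit. Section 9.2 requires grade, dates and causality for each event. Its lowest causality category reads "There is not a temporal relationship to study treatment".

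**The concern.** Section 9 is written for enrolled subjects. The photon controls are described as people who decline the study or are excluded from it. Their follow-up is stated in two ways: the study's own schedule in the synopsis and Section 5.3, and a cohort protocol that is not described in Section 8.0. A site cannot tell from this whether a photon patient needs Section 9 adverse-event pages, serious-event forms and causality grading, or from what date.

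The proton-photon comparison is the only concurrent one in Section 11; the others use published data. If one group's record opens at consent and the other's after radiotherapy, the groups differ in what was looked for as well as in what happened. Events never recorded cannot be recovered at analysis. Whom adverse-event collection covers is fixed by the protocol, so this is not a detail to be left to the statistical analysis plan.

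**Working it through.** The protocol states no figure to reproduce, so the check sets the sections side by side.

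| Item | Proton patients | Photon controls, unwilling or unsuitable | Photon controls, photon plan superior |
|---|---|---|---|
| Status | Enrolled by consent (5.9, 9.1) | Outside the study, willing to be followed (5.3) | Excluded from the study (8.0) |
| Follow-up rule | 5.6, 7.3 | Same as study patients (synopsis, 5.3) | A photon cohort protocol, not described (8.0) |
| Start of harm collection | Consent (9.1) | After photon treatment (synopsis) | Not stated |
| Baseline CTCAE symptoms | Yes (7.1) | Not stated | Not stated |
| Toxicity during treatment | Weeks 1, 3 and 5 (7.2) | Not stated | Not stated |
| Toxicity in follow-up | Every visit (5.6, 7.3) | Every visit, if the promise is kept | Depends on the cohort protocol |
| Section 9 forms and causality | Yes | Not stated | Not stated |

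**Where the groups agree.** For the first type of photon control, toxicity at follow-up visits is meant to be recorded as for proton patients.

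**Where they may differ.** The period before the end of radiotherapy is covered by Section 9 for proton patients and not clearly covered for photon controls. After treatment, the open points are whether Section 9 applies to photon controls and what the cohort protocol requires.

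**Length of the period.** Treatment should start within 4 weeks of registration (5.9). Radiotherapy should take 5 weeks and not exceed 6 (5.4).

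- Registration to end of radiotherapy for a proton patient: up to 4 + 5 = 9 weeks, or 4 + 6 = 10 weeks with interruptions.
- The first follow-up visit is 4 weeks later (5.6): up to 9 + 4 = 13, or 10 + 4 = 14 weeks from registration.

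Consent precedes registration by an unstated time, which adds to these figures.

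**Direction.** Suppose both treatments cause A recordable events per patient up to the end of radiotherapy and F afterwards. Under the literal reading, the proton count is A + F and the photon count at most F. The difference is (A + F) − F = A or more, although the true difference is zero. The error therefore counts against protons. The protocol gives neither A nor F, nor the size of the photon group, so this fixes the sign only.

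**The case against.** The strongest defence is that the synopsis and Section 5.3 already promise equal follow-up, with toxicity at every visit. The phrase in Section 8.0 may be loose wording for that same follow-up. The sentence in Section 9.1 says when surveillance starts and does not exclude photon patients. Someone moved to photons under Section 8.0 may already have signed consent and so be under surveillance. Section 9.3 asks for serious-event reports whatever treatment the subject received.

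This defence stands against three stronger readings that a reader might infer:

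- **That harms are in fact collected under different rules.** The text leaves this open. The cohort protocol cannot be seen and may carry identical rules.
- **That a share of photon events lost between visits can be computed from the visit spacing.** This needs a rule that a visit captures an event only if it is still present that day. No section says so. Sections 5.6 and 7.3 ask for new as well as continuing toxicity, and Section 9.2 also elicits proton events by questioning at contacts.
- **That every photon event must be graded unrelated, because these patients receive no study treatment.** Section 9 elsewhere refers to the radiotherapy or to therapy in general, and in places to a drug and an infusion, which looks like template wording. Section 11 names no comparison of treatment-related events.

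The defence does not close the gap. The synopsis promise covers only the time after photon treatment. Section 9.3 still speaks of a subject, the term whose scope is in doubt. Nothing says whether surveillance continues for a consented patient who is then excluded.

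**Conclusion.** The point holds as a matter of what the protocol fails to secure. Sections 5.3 and 8.0 and the synopsis conflict on how photon controls are followed, and Section 9 does not say that it covers them. Followed literally, the text gives proton patients surveillance from consent to the End of Study Visit, and photon controls at most follow-up toxicity after treatment. A pooled count could then favour photons on a primary objective.

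The size of the bias cannot be estimated from the document. What can be stated is its direction and the length of the clearly uncovered period: up to 9 to 10 weeks from registration to end of radiotherapy. This rests on two assumptions: that sites apply Sections 8.0 and 9.1 as written, and that the comparison pools events over all periods. If sites already use the Section 9 forms for photon controls from consent, the wording still needs correcting but the data are sound. The change should be made, since it is cheap and missed events cannot be restored later.

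**What to change.** 1. **Section 8.0:** reconcile with the synopsis and Section 5.3, so that every consenting photon control is followed under Sections 5.6, 7.3 and 9 of this protocol. Remove the reference to a photon cohort protocol.
2. **Section 9:** state that *subject* includes photon controls from the date of their own consent, and that *study treatment* means the radiotherapy received, proton or photon.
3. **Section 11:** restrict the proton-photon toxicity comparison to the period and recording form common to both groups, with all-cause events as the main comparison. Report proton events outside that period descriptively, without a photon comparator.

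The cost is a wording amendment and somewhat more adverse-event and serious-event data entry for photon patients. Acute events recorded only in proton patients drop out of the comparison, though they are still reported. No dose or clinical rule changes. For photon patients already treated under the present wording, item 3 protects the comparison where earlier events were not recorded.

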### 8.1 Fractionation and duration

Proton therapy will be given with pencil beam scanning (PBS) with proton energies in the range of 60 – 230 MeV at reference point according to ICRU 78.

For details on fractionation and treatment see section 5.3

Patients with a photon plan superior to the proton plan will receive fractionation and total dose according to local routine

### 8.2 Planning Target Volume

The different volumes of interest shall be defined in agreement with ICRU 78.

OAR's: heart, LADCA ,lung, spinal cord, esophagus

Gross Tumour Volume (**GTV**):

Visible tumour growth

Clinical Target Volume (**CTV**):

Post-operative tumour bed and/or defined margin to GTV: 0,5 cm to lung tissue and 1 cm elsewhere. Adjustment to airways, big vessels, bone will be performed. No adjuvant volumes, except for pleura/pericardium in between separate GTV's (stage IVa)

### Internal Target Volume (**ITV**)

The ITV volume includes CTV in all breathing phases defined according to local routines

### Planning Target Volume (**PTV**):

Includes ITV + 5 mm margin. PTV is used for dose prescription and reporting according to ICRU recommendations

The volumes of GTV, CTV, ITV and PTV shall be recorded in the CRF.

## 8.3 Doses to organs at risk

- Spinal cord

The maximum dose to the spinal cord is 48 Gy EQD2. The spinal cord shall be defined as the content of the spinal canal.

- Lung

Normal lung tissue is to be spared as much as possible. The volume of the lung (minus GTV) that should not receive doses above 20 Gy should be  $\leq 35\%$  ( $V_{20} < 35\%$ ). Dose-volumes histograms should be performed and the percentage of the lung volume minus GTV receiving a dose  $>5$ ,  $>20$  and  $>40$  Gy as well as mean lung dose shall be recorded ( $V_5$ ,  $V_{20}$ ,  $V_{40}$ , MLD)

- Esophagus

The esophagus shall be delineated from the esophageal entrance to cardia. The mean dose should be  $< 45$  Gy EQD2. The mean dose as well as the volume of the esophagus receiving  $> 50$  Gy EQD2 ( $V_{50}$ ) shall be recorded.

- Heart

The whole heart shall be delineated including the atriums and chambers but not the great vessels. No constraint is used, but the aim is to keep the dose as low as possible. Mean dose and volume receiving  $> 10$  Gy EQD2,  $> 20$  Gy EQD2 and  $> 40$  Gy EQD2 (MHD,  $V_{10}$ ,  $V_{20}$ ,  $V_{40}$ ) shall be recorded.

- LADCA

LADCA (Left Anterior Descending Coronary Artery) shall be delineated. No constraint will be used but  $D_{2\%}$  and  $D_{mean}$  shall be recorded

#### 8.4 OAR priority

**Table 2 Prioritized dose volume objectives and constraints in EQD2**

Priority	Volume	Objectives and constraints in biological dose Gy(RBE)	Objectives and constraints in physical dose Gy
1	Spinal cord	48	43.64
2	Lung (total)	$V_{20} < 35\%$	$V_{18.2} < 35\%$
3	Esophagus	Mean dose $< 45$	Mean dose $< 40.1$
4	GTV	$D_{100\%} > 100\%$	$D_{100\%} > 100\%$
5	CTV / ITV	$D_{98\%} > 95\%$	$D_{98\%} > 95\%$
6	PTV*	$D_{2\%} < 105\%$ $D_{98\%} > 95\%$	$D_{2\%} < 105\%$ $D_{98\%} > 95\%$
7	Heart	As low as possible	
8	LADCA	As low as possible	

\*Dose volume objectives for PTV may be disregarded if other strategies like robust optimization are used to ensure CTV coverage

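### Table 2 prints the oesophagus mean-dose limit as 40.1 Gy physical; the protocol's own RBE of 1.1 gives 40.9 Gy

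*Protocol*

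**What the plan says.** Section 5.3 (Treatment Schedule) sets the conversion rule: "We have assumed that RBE for protons is 1.1". It then gives the physical equivalent of each prescription: "1.82 Gy OD, total dose 45.5 Gy" for 2 Gy(RBE) to 50 Gy(RBE), "2.09 Gy OD, total dose 52.25 Gy" for 2.3 to 57.5, and "2.27 Gy OD, total dose 56.75 Gy" for 2.5 to 62.5. The title of Table 3 in section 8.5 repeats the RBE as 1.10.

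Table 2 in section 8.4 sets out organ and target limits by priority. One column is in Gy(RBE) and the other is headed "Objectives and constraints in physical dose Gy". Three organ rows carry figures in both columns:

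- spinal cord: 48 and 43.64
- lung: V20 and V18.2, each below 35%
- oesophagus: mean dose below 45 and, in the physical column, "Mean dose $< 40.1"

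Section 8.3 gives the oesophagus mean-dose limit only as 45, with no physical figure. The Methodology entry of the Synopsis says that doses are recorded in Gy(RBE).

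**The concern.** The two columns of Table 2 should state the same limit in two units. For the oesophagus they do not, so the protocol holds two different thresholds for one constraint.

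The figure is one that planners use. Table 2 ranks the oesophagus third, ahead of GTV, CTV/ITV and PTV coverage. Section 8.0 also makes it a condition for included patients that the prescribed dose can be given without breaching the organ doses. A planner who worked from the physical column would hold the oesophagus to a tighter limit than the one in section 8.3, and in a borderline case could give up target coverage to meet it. Table 2 does not itself say which column governs.

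**Working it through.** **Rule.** Physical dose = dose in Gy(RBE) / 1.1 (section 5.3). Because this RBE is one constant, the rule applies to a mean dose exactly as it does to a point dose, whatever the dose distribution in the organ.

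**Reproducing the protocol's other conversions.**

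| Place | Gy(RBE) | Divided by 1.1 | Printed | Deviation |
|---|---|---|---|---|
| 5.3, radical surgery, per fraction | 2 | 1.818 | 1.82 | +0.10% |
| 5.3, R1, per fraction | 2.3 | 2.091 | 2.09 | −0.04% |
| 5.3, inoperable/R2, per fraction | 2.5 | 2.273 | 2.27 | −0.12% |
| 5.3, radical surgery, total | 50 | 45.455 | 45.5 | +0.10% |
| 5.3, R1, total | 57.5 | 52.273 | 52.25 | −0.04% |
| 5.3, inoperable/R2, total | 62.5 | 56.818 | 56.75 | −0.12% |
| Table 2, cord | 48 | 43.636 | 43.64 | +0.01% |
| Table 2, lung | 20 | 18.182 | 18.2 | +0.10% |
| Table 2, oesophagus | 45 | 40.909 | 40.1 | −1.98% |

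The totals in 5.3 are the rounded fraction dose times 25 (for example 1.82 × 25 = 45.5), which explains their small deviations. Rounding elsewhere never moves a figure by more than 0.12%.

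**Size of the slip.**

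- Difference: 40.909 − 40.1 = 0.809 Gy physical; 0.809/40.909 = 2.0%.
- Implied RBE: 45/40.1 = 1.122.
- Printed limit in Gy(RBE): 40.1 × 1.1 = 44.11, which is 45 − 44.11 = 0.89 Gy(RBE) below the first column.

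A mean from 44.1 up to 45 Gy(RBE) therefore passes on one column and fails on the other.

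**Could 40.1 come from another rule?**

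- *The rounded fraction factors of 5.3.* 45 × 1.82/2 = 40.95; 45 × 2.09/2.3 = 40.89; 45 × 2.27/2.5 = 40.86. None gives 40.1.
- *45 read as EQD2 and converted over 25 fractions.* Since 45/25 = 1.8 is below 2 Gy per fraction, the converted dose exceeds 45 for any alpha/beta. With assumed alpha/beta of 1 to 10 Gy it is 42.7 down to 41.5 Gy physical. This moves away from 40.1.
- *45 read as EQD2 and converted at the prescribed fraction size.* Physical dose = 45 × (2 + α/β)/(d + α/β)/1.1. For assumed alpha/beta of 2, 3 and 10 Gy this gives 40.91 at d = 2, 38.05 to 39.91 at d = 2.3, and 36.4 to 39.3 at d = 2.5. None gives 40.1. A freely chosen alpha/beta could be made to fit, but the cord row in the same column is 48/1.1 with no such correction, so this is not the column's rule.

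The protocol gives no alpha/beta; the values above are assumptions, used only to test whether 40.1 could arise this way.

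**The case against.** The best defence is that the physical column is not the working scale. Doses are recorded in Gy(RBE), Table 3 uses an RBE of 1.10, and section 8.3 states the oesophagus limit only as 45. On that view 40.1 is a companion figure that nobody need rely on. Section 8.3 also words the oesophagus limit as something that should be met, and Table 3 leaves the Table 2 organ parameters in the robustness test to clinical judgement. All of this stands and keeps the point minor. It does not make the entry right: Table 2 presents both columns as objectives and constraints, and one of them is wrong.

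The tables were read from PDF by a program, so a misread digit cannot be fully excluded. The neighbouring entries (43.64, 18.2) read correctly, and nothing indicates a misreading here.

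A reader might go further and infer a second error. The caption says "Prioritized dose volume objectives and constraints in EQD2" and section 8.3 says "The maximum dose to the spinal cord is 48 Gy EQD2", yet the physical column is a plain division by 1.1 although the groups receive 2, 2.3 or 2.5 Gy(RBE) per fraction. The documents do not support calling this an error:

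- An EQD2 expressed in Gy(RBE) is a coherent quantity, so the caption and the column headings need not conflict.
- The group fraction sizes are prescriptions to the target. All three groups receive 25 fractions (50/2, 57.5/2.3, 62.5/2.5), and what matters for an organ is its own dose per fraction.
- Any conversion may be in the clinic's planning manual cited in section 8.5, which is not at hand.

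A reader might also infer a safety problem or a bias in the toxicity results. The slip tightens the limit, so it gives neither.

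**Conclusion.** The oesophagus entry in the physical column of Table 2 is wrong as written: it reads 40.1 Gy where the protocol's rule gives 40.9 Gy. A misprint of 40.9 is the likeliest cause. The error is 0.8 Gy physical (2.0%) and conservative. It matters only for proton plans with a mean oesophagus dose in the narrow band from 44.1 up to 45 Gy(RBE). The protocol does not allow the number of such plans to be estimated, and it is probably small. No endpoint, sample size or analysis changes.

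The conclusion rests on the RBE of 1.1 stated in section 5.3, on the first-column limit of 45 being the intended one (section 8.3 gives the same number), and on the PDF text having been read correctly. It does not depend on any alpha/beta value.

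**What to change.** Confirm the entry against the source file. Then, in section 8.4, Table 2, oesophagus row, change the physical mean-dose limit from 40.1 to 40.9 Gy.

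This is one table entry in the next amendment, with no cost to conduct. Until then, a short note to the planning team that the 45 Gy(RBE) limit applies would remove any doubt. No change to the EQD2 wording is proposed.
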